15. WITHDRAWAL OF SUBJECTS WITHOUT THEIR CONSENT*

Subjects will be withdrawn from the research if they appear to be unduly distressed

16. RISKS TO SUBJECTS*

In this research, the risks that result from study participation are considered minimal and primarily involve the risk of loss of confidentiality.

- **Risk of loss of confidentiality:** [name] is principally responsible for ensuring that there is no loss of confidentiality during the course of the study. Any loss that occurs despite these protections will be evaluated on an individual basis.

INVESTIGATOR STUDY PLAN

- **Risk of spirometry:** Spirometry is a routine, non-invasive clinical test that is commonly performed in children with asthma. This test has been used both clinically and in research without any adverse events.^{23,24} There are no risks associated with spirometry except for the potential for a slight dizzy feeling and/or temporary cough. These symptoms are not always present and are temporary. For this study the test is performed without the intent of yielding direct health benefit.
- **Risk of feeling uncomfortable answering questions:** Some subjects may feel uncomfortable answering certain questions (e.g., questions about family income) however subjects will be notified of this in the fact sheet (see fact sheet) and will be told that they are welcome to withdraw from the study at any time without penalty.

Given that this is a minimal risk study, the only foreseeable risks to the subjects include the possible loss of confidentiality. To address this, all participants will be given information on ways to contact [name] and the University of Massachusetts Medical School IRB.

17. POTENTIAL DIRECT BENEFITS TO SUBJECTS*

The potential benefit gained by study participants is the improvement of their personal health status through the prevention of asthma-related health risks for those with improved adherence to their preventive medication. In addition, each individual participant is contributing to the evaluation of childhood asthma interventions for school-aged children. Potential benefits to society and the larger community include the implementation of effective evidenced- based asthma interventions for school-aged children and increased capability to deliver intervention programs to children and families. These benefits are substantial in comparison to the minimal risk possible.

18. VULNERABLE POPULATIONS*

This research will involve children. The description below explains the importance of including children to perform this research and the safeguards, which will protect their rights and welfare.

Childhood asthma affects 12-15% of children in the urban United States with considerable morbidity and healthcare costs, despite aggressive efforts to address remediable causes. There exists extremely effective therapy for childhood asthma: inhaled corticosteroids (ICS). However, ICS are grossly underutilized with adherence rates at less than 20%, particularly in low-income, minority patients. Racial and socioeconomic disparities in childhood asthma are grave, with the highest rates of emergency room visits and hospitalizations for asthma occurring in low income and minority children. In spite of increasing recognition of the profound negative effects on children and families, which are mitigated by effective preventive therapy, including daily use of ICS, childhood asthma remains undertreated. Recognizing this gap, the NHLBI Expert Panel on Asthma emphasizes that asthma self-management is essential and there have been three successfully conducted trials of school-supervised ICS therapy in school-aged children.

Despite their success at improving ICS adherence rates and asthma symptoms, these research-tested interventions have not been adopted in real-world practice. This is due in part to high cost and high intensity approaches that are not feasible in the real world. This study seeks to

INVESTIGATOR STUDY PLAN

investigate a practical strategy (the Asthma Link™ program) to promote the uptake of school-supervised asthma therapy, which has been found to be safe and efficacious, into regular practice. This study will directly inform a large-scale cluster randomized controlled trial trial to test the effectiveness and implementation of Asthma Link with the goal of improving childhood asthma outcomes on a large public health scale.

- The parent/legal guardian will provide verbal consent for both the child to participate in the study and for them to participate in the study.
 - Research staff will mail interested families the fact sheet and contact them by phone to explain the study and describe the parent/legal guardian and child's potential role. The confidentiality of all collected information will be emphasized, and it will be explained that the child's care in the pediatric practice will in no way be affected by whether or not they participate in the study. The parent/legal guardian and child will be provided the opportunity to have questions answered by the research staff. If interested, parental/legal guardian consent and child assent will be requested and provided verbally during the call.
 - All questions will be answered before a parent gives verbal consent and child gives verbal assent, which will serve as the overt agreement to participate.
 - We will not enroll an individual if there is any sign of unwillingness to participate.
 - If a person is not eligible for the study or not willing to participate, they will not be consented or assented.
- Subjects will be withdrawn from the research if they appear to be unduly distressed.

We will obtain permission from one parent/legal guardian who will be joining the study with the child given that this is a minimal risk study.

Research staff will mail interested families the fact sheet and HIPAA authorization and contact them by phone to explain the study and describe the parent/legal guardian and child's potential role using a standardized information sheet. The confidentiality of all collected information will be emphasized, and it will be explained that the child's care in the pediatric practice will in no way be affected by whether or not they participate in the study. The parent/legal guardian and child will be provided the opportunity to have questions answered by the research staff. If interested, parental/legal guardian consent and child assent will be requested and provided verbally if the adult and child are both available at the time of the phone call.

We will answer all questions the child and parent/legal guardian may have prior to the child giving verbal assent.

- We will not enroll a child if there is any sign of unwillingness.
- We will not obtain verbal consent or assent for anyone who is not eligible or not willing to participate.

INVESTIGATOR STUDY PLAN

This research may also involve women who are or may become pregnant. No inducements, monetary or otherwise will be given to any pregnant woman participating in this study to terminate her pregnancy. The PI and the RC will have no part in any decisions as to the timing, method, or procedures used to terminate a pregnancy. Also, the PI and the RC will have no part in determining the viability of a neonate in this study. Given that this is a minimal risk study, we believe that this study poses no risk to a pregnant woman or the fetus and does not require any additional safeguards.

19. MULTI-SITE RESEARCH*

We will be recruiting patients from 4 pediatric offices. The physicians and staff in these practices will not:

- a. Obtain data about subjects through interaction for research purposes
- b. Obtain informed consent or assent of subjects to take part in the research
- c. Obtain identifiable private information about subjects for research purposes.

The practices performed by the physicians and office staff for enrollment in Asthma Link are considered good clinical practice based on the evidence described previously for school-supervised asthma therapy.¹³⁻¹⁵

20. COMMUNITY-BASED PARTICIPATORY RESEARCH*

N/A

21. SHARING OF RESEARCH RESULTS WITH SUBJECTS*

We will ask participants if they are interested in receiving a summary of the study findings. If they are, they will be added to an email list (a mailing address will be obtained for anyone who prefers this to an email address). Once the study has been completed, we will send a lay summary of the results to participants who indicated interest

22. SETTING

This pilot feasibility study will take place in 4 Pediatric Primary Care practices in Worcester MA: Benedict Pediatrics, Worcester Pediatrics, Quality Kids and Harding Pediatrics. These particular sites were selected due to their high rates of asthma and matching for relevant demographics. We have worked with these sites in [name] prior FITLINE study. If there are logistical issues with any of these practices after commencement of funding, we have identified 4 alternative practices in Worcester as backups.

23. RESOURCES AVAILABLE

This study includes the PI, research coordinator, research assistants, statistician and senior mentor. Collectively the staff has over 40 years of clinical research experience at UMMS. The roles of each research staff member is listed below:

Principal Investigator (PI) (0.75 FTE): This position requires advanced training in Pediatric Pulmonology, research design and methods. The PI is responsible for ensuring that all team members have current CITI training, appropriate training for their respective

INVESTIGATOR STUDY PLAN

roles, including knowledge of the study protocol and procedures for maintaining confidentiality. This person will oversee all aspects of the study, data acquisition, and data analysis.

Research Coordinator (0.6 FTE): This position is a specialized research professional working with and under the direction of the clinical Principal Investigator (PI). The Research Coordinator supports, facilitate and coordinate the daily clinical trial activities and plays a critical role in the conduct of the study. The responsibilities include: maintaining records, handling IRB submissions, data management, and performing any other study related procedures that fall within their scope of practice only after receiving the appropriate training required to perform the procedures.

Research Assistants (0.2 FTE): Responsibilities include support of study recruitment, data management, data analysis, and other study related activities deemed appropriate by the PI.

Statistician (0.01 FTE): This position requires training in statistics. The statistician will be responsible for data analysis and performing any other study related procedures that fall within their scope of practice only after receiving the appropriate training required to perform the procedures.

Senior Mentor (0.01 FTE): A Ph.D, Senior level investigator who will dedicate her time in-kind to oversight of this project

All study staff will be supervised by the PI and will have completed CITI/GCP certification. All persons assisting with the research will be trained and monitored by either the PI or the Research Coordinator and will be given copies of the procedures for performing this research.

24. LOCAL RECRUITMENT METHODS

Justify the feasibility of recruiting the required number of suitable subjects within the given recruitment period. For example, how many potential subjects do you have access to? What percentage of them do you need to recruit?

Feasibility of Recruitment: Rates of asthma approximately range from 15%-25% among the practices' patients, with a mean of 18.5%. Given this rate and number of patients, we are very confident that we will be able to recruit 13 families per practice over the course of the one and a half-year recruitment period.

Describe when, where, and how potential subjects will be identified and recruited. If recruiting in a clinical setting, will clinical staff ask potential subjects if it's ok for study staff to approach? If recruiting by mail, will letters come from the subject's clinician or clinic head?

For the sites that are randomized into the intervention arm of the study, a one page flyer for the clinical Asthma Link™ program will be placed in each of the exam rooms in the clinics and will encourage families to ask their providers about Asthma Link™ if they have a child who has asthma. The flyer will only advertise the clinical Asthma Link™ program. Additionally, triage nurses at these sites may remind providers to screen potentially eligible patients for the clinical Asthma Link™ program when scheduling sick visits related to Asthma or breathing

INVESTIGATOR STUDY PLAN

problems. During the clinic visit, the pediatric provider will give the family a one-page description of the study and, if interested, will send a referral to the study. Research staff will mail the family the fact sheet and HIPAA authorization, contact them by phone to explain the study, and obtain verbal consent for those interested. Research staff will send an email link to access the survey to families who provide verbal consent. The 4 pediatric practices participating in the trial estimate 7,462 children total in their practices between children in grades 1-6; with a conservative estimate of 15% with asthma symptoms, this provides approximately 1,119 children from which to recruit 40 children into the trial, making recruitment highly feasible.

Describe how individuals will be screened for eligibility. Will any identifiers be recorded? If so, when will identifiers be de-linked from the data and when will identifiers be completely destroyed? Be sure to address individuals who enroll and individuals who turn out to be ineligible or who decline to participate.

The fact sheets and the HIPAA authorization form will be mailed to the potential participants with a letter saying that the Research Coordinator will call them. The Research Coordinator will contact the parent by phone to explain the study and describe the parent/legal guardian and child's potential role using a standardized information sheet. The Research Coordinator will answer any questions about the study and **obtain** verbal consent. Once the parent provides consent, the Research Coordinator will obtain verbal assent from the child. The Research Coordinator will then email the link to sign the HIPAA authorization. Once the HIPAA authorization is signed, the Research Coordinator will then email the link to complete the survey via REDCap. The Research Coordinator will only call the family five times. The first time a message will not be left. The second, fourth and fifth time a message will be left saying "This is X from the University of Massachusetts Medical School. I am calling about the material I sent you. Please call me back at X. (please see uploaded flyer and phone script). Enrollment will not begin until IRB has approved these materials. Individuals who decline to be contacted or who decline to participate in the study will not be contacted.

Describe the amount, method, and timing of any payments to subjects.

To compensate participants for their time, and to incentivize participation in the completion of all assessments, we will provide compensation to each parent-child dyad in the form of gift cards to a local retailer (i.e., Target or Wal-Mart). Compensation will be divided through the study period (a \$30 gift card for each parent-child dyad on enrollment and completion of baseline assessment, another \$30 gift card at 3-month assessment, a \$30 gift card at 6-month assessment, and a \$40 gift card at the 12 month assessment). We will also be mailing families with a short hand-written thank you note and 'prize' after the 3 month survey (stickers), 6 month survey (small toy prize), at the 9 month time point (magnet or postcard with reminder for 12 mo survey), and after the completion of the 12 month survey (completion certificate). All mailings will be in a sealed envelope to protect confidentiality. Pediatric practice sites will be provided lunch during their information session for the research study which will be funded by the NIH KL2TR001454 award and will be considered separate from the subject compensation.

School nurses participating in the study will receive a \$35 honorarium for their help with completing the School Nurse checklist and for completing the brief surveys.

INVESTIGATOR STUDY PLAN

Asthma Champions will receive \$15 for completing the baseline survey and \$20 for completing the follow-up AC survey for a total honorarium of \$35.

We will provide coffee and donuts to the medical provider's practice if all participating providers complete both the baseline and follow-up surveys.

Upload copies of recruitment materials, including flyers, emails, letters, phone scripts, etc., to eIRB. For advertisements, upload the final copy of printed advertisements. When advertisements are taped for broadcast, provide a link to the final production of the audio/video tape. You may submit the wording of the advertisement prior to taping to preclude re-taping because of inappropriate wording; however, the IRB must review and approve the final audio/video tape.

See flyer and phone screen

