6. INCLUSION AND EXCLUSION CRITERIA*

Child eligibility criteria for enrollment in Asthma Link™ (established clinical program):

- (1) children aged 6-17 years (enrolled in grade 1-12)
- (2) prescribed daily inhaled corticosteroid (ICS) for asthma;
- (3) 1 or more courses of oral steroids in the past 2 years OR 1 or more hospitalizations or ED visits for asthma in the past 2 years OR Asthma Control Test (ACT) score <19 OR 1 or more sick or urgent care visits for asthma (including telehealth) in the last year
- (4) parent/child report of poor ICS adherence on adherence checklist- i.e. child or parent says “Yes” when provider asks if they have difficulty remembering to take their medication or if they regularly take medication holidays or breaks;
- (5) able and willing to assent;
- (6) parental permission
- (7) English or Spanish speaking.

STUDY INCLUSION/EXCLUSION Criteria:

Child Inclusion criteria:

- 1) Meet the eligibility criteria for Asthma Link (as described above) with exception to (7)
- 2) Enrolled in Asthma Link™ (if randomized to the Asthma Link™ Condition)
- 3) Able and willing to provide informed assent
- 4) Must be English or Spanish speaking

Child Exclusion criteria:

- (1) Unable or unwilling to provide informed assent
- (2) Diagnosis of a serious co-morbid illness during the past 5 years
- (3) Developmental delay that would prevent study participation.
- (4) Planning on moving from primary residence or moving outside of the school district in the next 1 year
- (5) A sibling to a child participating in this study

Parent Inclusion criteria are:

- 1) Parent/guardian to patient
- 2) 18 years or older
- 3) Able to understand and communicate in English or Spanish

INVESTIGATOR STUDY PLAN

- 4) Able and willing to provide informed consent.
- 5) May or may not be or become pregnant

Medical Provider Inclusion criteria are:

- 1) Able and willing to provide informed consent

Medical Provider Exclusion criteria are:

- 1) Unable or unwilling to provide informed consent

School Nurse Inclusion criteria are:

- 1) Able and willing to provide informed consent

School Nurse Exclusion criteria are:

- 1) Unable or unwilling to provide informed consent

Asthma Champion Inclusion criteria are:

- 1) Able and willing to provide informed consent

Asthma Champion Exclusion criteria are:

- 1) Unable or unwilling to provide informed consent

Adults lacking capacity and prisoners are also excluded

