11. PROCEDURES INVOLVED*

Randomization. Two groups of two practices (4 practices in total) will be matched based on comparable size and percent of minority patients. Within each pair, practices will be randomly allocated to Asthma Link or the comparison condition, using a computerized function. This will result in two practices randomized to the Asthma Link condition and two practices randomized to the Enhanced Usual Care comparison condition.

Recruitment will be performed from each practice site until the target n=72 parent-child dyads (18 per site) are recruited. (see section 13 on “Sample size calculation”) Recruitment will begin during the 2021-2022 academic school year.

Procedure Steps:

1. Research coordinator (RC) identifies potentially eligible patients (children aged 6-17 years (enrolled in grade 1-12) years and prescribed a daily inhaled corticosteroid per medical record from most recent visit scheduled for a clinic visit) through the practice's office scheduling and medical record system (e.g., Epic). RC will also collect that patient's name, DOB, mailing and email addresses, phone number, insurance type (as a proxy for socioeconomic status), list of

INVESTIGATOR STUDY PLAN

medications, number of emergency room visits, number of hospital admissions and number of oral steroid courses for asthma relief.

2. RC creates a Lilac Form for any potentially eligible patients as described above. (Lilac form is an indicator to the medical provider seeing the patient that this patient is potentially eligible for study.)

3. Asthma Link condition: As part of clinical practice, medical provider will determine if patient is struggling with taking daily asthma medicine. If YES, then will introduce Asthma Link by saying “There is a clinical program that allows for your child to receive their daily asthma medicine at school supervised by the school nurse.” Child can be enrolled in Asthma Link per the usual clinical steps (see Asthma Link steps).

- After they are enrolled in Asthma Link, medical provider will give family one-page description of study (see Flyer) and state “Researchers at UMass are performing a study of children who are participating in Asthma Link, would you be interested in hearing more?”

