3a. Enhanced Usual Care comparison condition: Medical provider will determine if patient is struggling with taking daily asthma medicine, if YES, the provider will give family a one-page description of study (see Flyer) and state “Researchers at UMass are performing a study of children with asthma to learn about how to support them in taking their every day asthma medicine, would you be interested in hearing more?”

- Attached to the “Flyer” will be the Authorization to Contact form. (see Authorization to Contact form)
- If the parent agrees, the Lilac form with the family’s information is faxed to the Research Coordinator. The pediatric office will fax this form with a confidential cover form.
- The fact sheet will be mailed to the parent with a letter saying that the Research Coordinator will call or text them (see Fact Sheet).
- The Research Coordinator will only call the parent five times. The first and third time a message will not be left, but a text message will be sent stating “This is X from Asthma Link, can I call you at TIME?” The second, fourth, and fifth time a message will be left saying “This is X from the University of Massachusetts Medical School. I am calling about the material on Asthma Link I sent you. Please call me back at X.”
- A phone screen will be conducted to ensure study inclusion criteria (see phone script).
- The Research Coordinator will obtain informed consent from eligible participants, including parental permission for their child to participate, child assent to participate, and parental consent to participate. (see sections 30, 31 on Consent)
- After all questions are answered regarding the study by the parent, the Research Coordinator will send the baseline survey via email to the participant to be completed by the parent and child together or will complete the survey over the phone with the child and parent.
- The Research Coordinator will then access the child’s medical record and obtain the discharge summaries, the emergency service records, the office/clinic notes, the problem list, the pulmonary studies, the child’s list of medications, and the child’s height and weight (to help interpret the spirometry data).
- The Research Coordinator will then call the child’s pharmacy to obtain refill history for their daily ICS inhaler.

INVESTIGATOR STUDY PLAN

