SURVEY – MEDICAL PROVIDER – 5 MINUTES _See uploaded medical provider baseline and end-of-intervention surveys. The medical provider survey will include the following constructs: acceptability, cost, and sustainability. All surveys will be completed either on-line using RedCap (please see data management section) or over the phone with the research coordinator. We are using emails and/or phone calls to deliver and collect these surveys.

SURVEY- ASTHMA CHAMPION- 5 MINUTES _See uploaded asthma champion baseline and end-of-intervention surveys. This will include the same constructs of acceptability, cost and sustainability. Surveys will be completed either on-line using RedCap (please see data management section) or over the phone with the research coordinator. We are using emails and/or phone calls to deliver and collect these surveys.

INVESTIGATOR STUDY PLAN

We will be accessing the practice's medical record system (same system as above, e.g., Epic) to obtain documentation of the child's emergency room visits, hospital admissions, and oral steroid courses at the baseline time point (recording the number of events for the 6 months prior), 3 month, 6 month, and 12 month time points (recording the number of each of these events for the 3 or 6 months prior.). This data will also be collected 12 months following the completion of the 12 month survey in order to observe for sustained impact on health outcomes and to see if engagement in Asthma Link continues beyond one year. This data will be directly put into the RedCap database without any downloading of information. (please see data management section)

We will be contacting the child's pharmacy to obtain refill history of their daily ICS medication at baseline (obtaining the number of refills for the prior 6 months), 3, 6, and 12 months, and 12 months following the completion of the 12 month survey to assess for medication adherence. This data will be entered directly into the REDCap database.

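### Triage-nurse reminders at asthma sick visits are described only for intervention sites, so more Asthma Link children may enter around an acute episode, which can bias change-from-baseline comparisons and make recruitment counts less comparable

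*Combined protocol and SAP*

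**What the plan says.** Section 11 randomises practices, not children: "Within each pair, practices will be randomly allocated to Asthma Link or the comparison condition, using a computerized function". Children are identified by their practice and the research coordinator, and no step places this before allocation.

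One identification step is common to both arms. The coordinator searches for children in the age range with a daily inhaled steroid "per medical record from most recent visit scheduled for a clinic visit", and "RC creates a Lilac Form for any potentially eligible patients as described above". Nothing limits this to well visits or to sick visits. The provider then asks about adherence. In the comparison arm (step 3a): "Medical provider will determine if patient is struggling with taking daily asthma medicine, if YES", the study is offered directly. In the Asthma Link arm (step 3) the child is first enrolled in the clinical programme and only then told of the study.

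Section 24 adds two things, introduced by "For the sites that are randomized into the intervention arm of the study": an exam-room flyer for the programme, and the statement that "triage nurses at these sites may remind providers to screen potentially eligible patients for the clinical Asthma Link™ program when scheduling sick visits" for asthma or breathing problems. It describes neither for comparison sites.

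Criterion (3) in section 6 applies to both arms and can be met by "1 or more sick or urgent care visits for asthma (including telehealth) in the last year". Emergency department (ED) visits, admissions and oral steroid courses are taken from the medical record "at the baseline time point (recording the number of events for the 6 months prior"). Section 13 compares the arms by t-test (parametric or nonparametric) or Poisson regression. It names no baseline adjustment and does not say whether follow-up values or changes are compared.

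**The concern.** In the Asthma Link arm a prompt for the programme is also a prompt for the study, because programme enrolment comes first. A prompt tied to sick visits, present in one arm only and acting after allocation, can shift when in the course of illness children enter. Randomising practices cannot balance that.

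Children who enter around an acute episode tend to look better later whatever the programme does. If they are more common in one arm, that arm shows extra improvement from baseline through regression to the mean. Sections 5 and 13 make clear why this matters: the comparison group is there because earlier evidence was pre/post only, and the pilot's SDs and effect size are among the inputs to the large trial. Recruitment, a primary trial outcome in section 4, would also be counted under different referral prompts in the two arms.

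**Working it through.** The plan states no figure on this point, so there is nothing to reproduce. The check has three parts.

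**1. Where an acute episode reaches the baseline data.**
- *Event counts.* The look-back is 6 months, so a recent index episode falls inside it. It adds to the count only if it produced an ED visit, an admission or a steroid course. A sick visit alone is not a counted event.
- *ACT and FEV1.* These are not measured at the visit. Sections 11 and 24 put a faxed form, a mailed fact sheet, up to five calls, consent and assent, and an electronic HIPAA signature before the survey. Spirometry is done at school. Part of any dip may have resolved by then, so the event counts are the clearest route.

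**2. Illustrative size in a change-from-baseline comparison.** All inputs here are assumptions:
- sick-visit entries: 30-50% in Asthma Link, 10-20% in comparison;
- transient ACT deficit at baseline: 2-4 points; ACT SD: 4;
- share of sick visits that bring a steroid course: 30-50%.

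Excess share = Asthma Link share − comparison share. Minimum 0.30 − 0.20 = 0.10; maximum 0.50 − 0.10 = 0.40.

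Spurious difference in ACT change = excess share × deficit:
- low: 0.10 × 2 = 0.2 points, 0.2 / 4 = 0.05 SD;
- high: 0.40 × 4 = 1.6 points, 1.6 / 4 = 0.4 SD.

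Excess baseline steroid courses = excess share × share with a course:
- low: 0.10 × 0.30 = 0.03 per child, or 36 × 0.03 ≈ 1 course per arm;
- high: 0.40 × 0.50 = 0.20 per child, or 36 × 0.20 ≈ 7 courses per arm.

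For scale, take 36 dyads per condition, 18 per practice and ICC 0.01 from section 13. Design effect = 1 + 17 × 0.01 = 1.17. If the SD of change is 1 SD (baseline/follow-up correlation 0.5, assumed), SE of the arm difference = √(2 × 1.17 / 36) ≈ 0.25 SD. With no true effect, a nominal 5% two-sided test rejects with probability Φ(b/SE − 1.96) + Φ(−b/SE − 1.96):

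| Bias b (SD) | Rejection rate |
|---|---|
| 0.05 | about 5% |
| 0.20 | about 12% |
| 0.40 | about 35% |

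**3. Dependence on the analysis.** A large-sample simulation with no programme effect and correlation 0.5 compared three analyses under two mechanisms. *Transient*: 10-50% extra entrants with a baseline worsening of 0.5-1.0 SD that is gone at follow-up. *Selection*: 25-50% extra entrants chosen for a poor baseline value, so their asthma is also persistently worse on average.

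| Analysis | Transient | Selection |
|---|---|---|
| Change from baseline | favours Asthma Link by 0.05-0.50 SD | favours Asthma Link by 0.19-0.38 SD |
| Follow-up only | about no bias | against Asthma Link by 0.20-0.38 SD |
| Adjusted for baseline value | about half of the change-score bias remains | essentially none |

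The direction therefore depends on a choice that section 13 leaves open, and baseline adjustment alone may remove only part of the bias.

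**The case against.** The case against is substantial, and several parts of it stand.

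- *The reminder is permissive.* Section 24 says nurses may give it, and the coordinator's search covers any scheduled clinic visit in both arms. A reader might infer that entry-visit type differs by arm by design, or that the schedule search misses short-notice sick visits. The documents support neither: use of the reminder is unknown, and the frequency of the search is not stated.
- *Eligibility is the same in both arms.* Criterion (3) has several broad alternatives, and a sick visit can satisfy it in either arm. Some regression to the mean is therefore shared; only the excess is differential.
- *Not every sick-visit child carries a baseline event or a low ACT and FEV1.* The look-back rule and the delay before baseline measurement rule out that stronger reading.
- *Visit type may be recoverable.* Section 11 has the coordinator obtain office notes and emergency records after consent, in both arms. The Lilac form is not reproduced, so its fields cannot be judged. What is missing is a stated plan to extract and use visit type.
- *Consequences are bounded.* The health analyses are exploratory, and section 13 warns against relying on pilot effect sizes and will combine them with outside evidence. It nevertheless lists effect size and SD among the inputs to the larger trial.
- *The referral paths already differ* between steps 3 and 3a, apart from triage. That is true, but the sick-visit prompt adds a difference tied to illness state, and it can be removed without changing the programme.

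None of this supplies a comparison-site counterpart to the reminder.

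**Conclusion.** The point holds in a limited form. The plan describes a sick-visit prompt in one arm only, acting after practices are allocated, in a path where programme enrolment precedes the study offer. It may raise the share of Asthma Link children who enter around an acute episode. The clearest effect is on the 6-month baseline event counts; the effect on ACT and FEV1 may be weaker.

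The illustrated size is 0.2-1.6 ACT points and 0.03-0.20 steroid courses per child. Both ranges rest wholly on assumed shares and deficits, and the upper ACT values do not allow for recovery before the baseline survey. Against an SE of about 0.25 SD, the ACT bias ranges from negligible to about one and a half standard errors.

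A reader might conclude that the trial will show a false benefit. The documents do not support that: the excess is unmeasured, the bias favours Asthma Link only in change-from-baseline or pre/post contrasts, and the planned contrast is not stated. This is a cheap improvement to recruitment counts and exploratory estimates, not a flaw that undermines the pilot.

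**What to change.** 1. Use the same triage prompt in all four practices. At comparison sites, word it as a reminder to ask about trouble taking daily asthma medicine, without naming Asthma Link.
2. Record index-visit type (asthma sick visit or other) and visit date for every referred child in both arms, for example as a field on the Lilac form.
3. Report visit type by arm alongside the recruitment counts.
4. State in section 13 whether follow-up values or changes are compared. In the exploratory health comparisons, adjust for the baseline value and visit type, or repeat them without sick-visit entrants as a sensitivity analysis. Note that adjustment may remove only part of the bias, which is why aligning the prompt comes first.

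Cost: a short instruction and slightly more triage work at two practices, one form field, and one or two model terms in a small sample. If the sponsor regards the reminder as part of the programme and keeps it in one arm, steps 2 to 4 still show whether an imbalance arose.
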